9.5 Analysis of secondary variables

9.5.1 Efficacy variables

For the secondary variable is the proportion of patients with increased level of non-sedentary daytime physical activity at 'end of study' compared to baseline. It will be analyzed by applying a logistic regression model with factors treatment and baseline NYHA class (NYHA II vs. III/IV) and the baseline value as further covariate. The Odds Ratio for the factor treatment and its 95%-confidence interval will be given. The analysis of this secondary variable will be performed in the FAS (with and without imputation of missing values described in [Section 9.4.3](#).) and additionally in the PP population with and without imputation of missing values.

All other secondary efficacy variables will be analyzed descriptively using the statistics for continuous and categorical data described in [Section 9](#) above. Additionally, two-sided tests of significance (with $\alpha = 0.05$) between the two treatment groups will be performed for all secondary endpoints, using appropriate testing procedures. Details to those statistical testing procedures will be defined in the SAP.

All statistical tests of secondary efficacy variables will be on an exploratory basis. Therefore, no multiple testing strategy will apply for these tests

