2 STUDY OBJECTIVES

[figure not shown]
Primary objectives

- To elucidate the change in physical activity as assessed by the distance walked in meters during the 6-minute walking test between baseline and 12 weeks of study drug treatment in sacubitril/valsartan vs. enalapril patients.
- To assess changes in daily non-sedentary daytime activity between baseline and after 12 weeks of treatment in sacubitril/valsartan vs. enalapril treated patients.

Secondary objectives

- To compare the proportion of patients with improved performance ($\geq 30m$) in the 6-minute walking test at week 12 between sacubitril/valsartan vs. enalapril treated patients.
- To demonstrate that sacubitril/valsartan is superior in improving exercise capacity as assessed by the six-minute walk test (6MWT) at week 12 in a subset of patients with baseline six-minute walk distance equal to or less than 300 meters
- To demonstrate that sacubitril/valsartan is superior in improving exercise capacity as assessed by the six-minute walk test (6MWT) at week 12 in the patients with baseline six-minute walk distance between 100-450 meters.
- To assess changes from baseline (week 0) in exercise capacity assessed by means of the 6-minute walking test at weeks 4, 8 and 12

- To compare the effects of sacubitril/valsartan vs. enalapril on patients' symptom progression by means of the Patient Global Assessment (PGA) questionnaire at week 4, week 8 and week 12.
- To assess dynamics of changes from baseline in daily non-sedentary daytime physical activity in sacubitril/valsartan vs. enalapril treated patients in weekly and two-weekly intervals.
- To assess changes from baseline in mean daily non-sedentary daytime physical activity classified by its intensity for sacubitril/valsartan vs. enalapril treated patients after week 4, week 8 and week12.
- To assess the difference in non-sedentary daytime physical activity between sacubitril/valsartan vs. enalapril treated patients during the treatment period (weeks 0 to 12).
- To assess changes from baseline on M6min (an actigraphy-based measure of the peak six minutes of daytime physical activity) in sacubitril/valsartan vs. enalapril treated patients after week 4; week 8 and week 12.

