6.3.6 Secondary Efficacy Analyses

Proportion of patients with improved performance (≥ 30 m) in 6-minute walking test at week 12 compared to baseline. The comparison of patient groups will be carried out using logistic regression model with factors treatment and baseline NYHA class (NYHA II vs. III/IV) and the baseline value as further covariate. The Odds Ratio for the factor treatment and its 95%-confidence interval will be given.

Proportion of patients with improved performance (≥ 30 m) in 6-minute walking test at week 12 compared to baseline in a subset of patients with baseline 6-minute walk distance equal to or less than 300 meters. The comparison of patient groups will be carried out using logistic regression model with factors treatment and baseline NYHA class (NYHA II vs. III/IV) and the baseline value as further covariate. The Odds Ratio for the factor treatment and its 95%-confidence interval will be given.

Proportion of patients with improved performance (≥ 30 m) in 6-minute walking test at week 12 compared to baseline in a subset of patients with baseline 6-minute walk distance between 100-450 meters. The comparison of patient groups will be carried out using logistic regression model with factors treatment and baseline NYHA class (NYHA II vs. III/IV) and the baseline value as further covariate. The Odds Ratio for the factor treatment and its 95%-confidence interval will be given.

Score of 6-minute walking test will be summarised at baseline, week 4, week 8 and week 12. Change from baseline values will be presented. The comparison of patient groups at week 12 compared to baseline will be analyzed using a two sample (independent group) t-test or a non-parametric Mann–Whitney–Wilcoxon (Wilcoxon rank sum) test, where applicable.

Proportion of patients who show increased levels ($\geq 10\%$ increase) of non-sedentary daytime physical activity at week 12 compared to baseline. The comparison of patient groups will be carried out using logistic regression model with factors treatment and baseline NYHA class (NYHA II vs. III/IV) and the baseline value as further covariate. The Odds Ratio for the factor treatment and its 95%-confidence interval will be given.

PGA scores will be tabulated at week 4, week 8 and week 12. The comparison of patient groups at week 4, week 8 and week 12 will be analyzed using a chi-square test or Fisher's exact test, where applicable.

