M6min (an actigraphy-based measure of the peak six minutes of daytime physical activity) will be summarised at baseline, week 2, week 4, week 6, week 8, week 10 and week 12. Change from baseline values will be presented. The comparison of patient groups at week 12 compared to baseline will be analyzed using a two sample (independent group) t-test or a non-parametric Mann–Whitney–Wilcoxon (Wilcoxon rank sum) test, where applicable.

Proportion of patients with increased M6min (an actigraphy-based measure of the peak six minutes of daytime physical activity) compared to baseline at week 4, week 8 and week 12 will be tabulated. The comparison of patient groups will be presented and analyzed using a chi-square test or Fisher's exact test, where applicable.

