Table 14.2-10 Improved performance (≥ 30 m) in 6MWT for patients with baseline 6MWT between 100-450 meters: logistic regression model.
FAS population/FAS population subset patients without AE/SAE
Statistical (logistic model) by treatment group

Table 14.2-11 6-minute walking test: absolute and change between baseline at week 4, week 8 and week 12 by treatment group.
FAS population/FAS population subset patients without AE/SAE
Descriptive statistics and statistical analysis by treatment group

Table 14.2-12 Increased levels ($\geq 10\%$ increase) of non-sedentary daytime physical activity: proportion of patients at the end of study by treatment group.
FAS population
Descriptive statistics

Table 14.2-13 Increased levels ($\geq 10\%$ increase) of non-sedentary daytime physical activity: logistic regression model.
FAS population
Statistical (logistic model) by treatment group

Table 14.2-14 PGA score at week 4, week 8 and week 12 by treatment group.
FAS population
Descriptive statistics and statistical analysis by treatment group

Table 14.2-15 Patients who improved symptoms of HF as assessed by PGA: proportion of patients at week 4, week 8 and week 12 by treatment group.
FAS population
Descriptive statistics and statistical analysis by treatment group

Table 14.2-16 Mean daily non-sedentary daytime activity: absolute and change in weekly and two-weekly intervals by treatment group.
FAS population
Descriptive statistics and statistical analysis by treatment group

Table 14.2-17 Mean daily non-sedentary daytime activity: Proportion of patients at weekly and two-weekly intervals who show increased levels ($\geq 10\%$ increase) by treatment group.
FAS population
Descriptive statistics and statistical analysis by treatment group

Table 14.2-18 Mean daily light and moderate-to-vigorous non-sedentary daytime physical activity: absolute and change by week and treatment group.
FAS population

[figure not shown]
Table 14.2-19	Descriptive statistics and statistical analysis by treatment group Total weekly time spent in non-sedentary daytime physical activity: absolute and change by week and treatment group.
Table 14.2-20	FAS population Descriptive statistics and statistical analysis by treatment group Total weekly time spent in light non-sedentary daytime physical activity: absolute and change by week and treatment group.

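### SAP 6.3.6 states an arm comparison of 6MWT change and continuous M6min change only at week 12, in conflict with the objectives and its own table list, and re-tests the week-12 co-primary without adjustment

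*SAP*

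**What the plan says.** **Objectives.** SAP section 2 sets the 6MWT secondary objective as "To assess changes from baseline (week 0) in exercise capacity assessed by means of the 6-minute walking test at weeks 4, 8 and 12". The M6min objective is explicitly comparative: "in sacubitril/valsartan vs. enalapril treated patients after week 4; week 8 and week 12". Protocol Table 2-1 gives the same time points.

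**Analysis text.** SAP 6.3.6 summarises 6MWT at baseline and weeks 4, 8 and 12, then states: "The comparison of patient groups at week 12 compared to baseline will be analyzed using a two sample (independent group) t-test", with Wilcoxon as the alternative. Continuous M6min is summarised every two weeks, followed by the same restriction: "The comparison of patient groups at week 12 compared to baseline will be analyzed using a two sample".

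**Neighbouring endpoints in the same section.** PGA carries no such limit: "The comparison of patient groups at week 4, week 8 and week 12 will be analyzed using a chi-square test". The M6min responder proportion carries none either; its text reads: "compared to baseline at week 4, week 8 and week 12 will be tabulated. The comparison of patient groups will be presented and analyzed". Weekly and two-weekly activity is also compared between arms without a week-12 limit.

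**Table list.** SAP Appendix 1 has "Table 14.2-11 6-minute walking test: absolute and change between baseline at week 4, week 8 and week 12 by treatment group", and its label calls for statistical analysis as well as description. Table 14.2-22 (M6min at the same weeks) appears to carry the same label, although the layout of the list leaves the pairing uncertain.

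**Protocol rule.** Protocol 9.5.1 says that two-sided tests "between the two treatment groups will be performed for all secondary endpoints". It calls these tests exploratory and leaves the details to the SAP.

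**Primary analysis.** SAP 6.3.5 tests the week-12 change in 6MWT by ANCOVA with treatment, baseline NYHA class and baseline distance.

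**The concern.** The week-12 change in 6MWT is already a co-primary endpoint. What the secondary endpoint adds is weeks 4 and 8, and the analysis text states no arm contrast at either. It directs the test to the one visit that already has a better analysis.

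Two things are at stake. First, two programmers could follow the same SAP and produce different output: one working from section 6.3.6 would test week 12 only, and one working from the table list would test all three weeks. Protocol 3.6 describes the trial as a study of short-term effects from initiation to first maintenance of a stable dose, so the early walk-test contrasts are relevant to its aim. Second, the study report would carry two p-values for the same week-12 change in a co-primary measure, one adjusted and one not, with no rule for which to cite if they differ.

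**Working it through.** **1. The passages side by side**

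| Endpoint | Weeks in objective | Arm comparison stated in SAP 6.3.6 | Table list |
|---|---|---|---|
| 6MWT change | 4, 8, 12 | 12 only | 4, 8, 12 with statistical analysis (14.2-11) |
| M6min change | 4, 8, 12, between arms | 12 only | 4, 8, 12; apparently with statistical analysis (14.2-22) |
| M6min responder proportion | 4, 8, 12 | no week-12 limit | 4, 8, 12 (14.2-23) |
| PGA score | 4, 8, 12 | 4, 8, 12 | 4, 8, 12 with statistical analysis (14.2-14) |

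Only the first two rows conflict. The 6MWT time points are also unsettled elsewhere: Protocol 9.8 describes the primary 6MWT change as covering weeks 4, 8 and 12, and SAP 4.2 gives both that and week 12 alone.

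**2. Reproducing the plan's figure.** Inputs from SAP 4.2: difference 35 m, SD 114 m, two-sided alpha 0.05, power 90%. The normal approximation gives 223 per group and the exact two-sample t calculation gives 224, the stated number.

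**3. Precision of an early contrast.** Take 300 per arm (SAP 4.2) and assume an SD of change of 114 m at every visit.
- SE = 114 × √(2/300) = 9.31 m
- 95% CI half-width = 1.96 × 9.31 = 18.2 m
- Power of an unadjusted test: 36% at 15 m, 57% at 20 m, 77% at 25 m, 90% at 30 m, 96% at 35 m

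No extra patients are needed for estimates at weeks 4 and 8.

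**4. The second week-12 test.** Let ρ be the correlation of baseline with week-12 distance, with equal variance σ² at both visits.
- Variance of change: 2σ²(1 − ρ)
- ANCOVA residual variance: σ²(1 − ρ²)
- Ratio of SEs, ANCOVA to change score: k = √((1 + ρ)/2). This is also the correlation of the two estimates.

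At ρ = 0.5, k = 0.866 and the ANCOVA SE is 0.866 × 9.31 = 8.06 m. One million simulated trials, 300 per arm, SD of change 114 m:

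| True difference | ρ | Power, t-test | Power, ANCOVA | Disagree on p < 0.05 |
|---|---|---|---|---|
| 35 m | 0.5 | 96% | 99% | 3.0% |
| 35 m | 0.7 | 96% | 98% | 2.4% |
| 20 m | 0.3 | 58% | 76% | 24% |
| 20 m | 0.5 | 57% | 70% | 19% |
| 20 m | 0.7 | 58% | 65% | 13% |
| 20 m | 0.9 | 58% | 60% | 7% |
| 0 | 0.5 | – | – | 4.7% |

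With no true difference and ρ = 0.5, at least one of the two tests is significant in 7.3% of trials (6.1% to 7.7% for ρ from 0.9 to 0.3).

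**5. The price of three looks.** Three independent 5% tests give 1 − 0.95³ = 14.3% for any false positive. With an assumed correlation of 0.8 to 0.5 between the test statistics, the figure is about 10% to 13%.

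**The case against.** **The table list already covers weeks 4 and 8.** Table 14.2-11 asks for statistical analysis at those visits, SAP 6.3.2 gives a general t-test or Wilcoxon rule and adds 95% CIs to secondary continuous summaries, and Figure 14.2-1 plots every visit. This stands in part. It means that the defect is a conflict between text and table list, and that one cannot say the early data will go unused. It does not cure the text, which is specific where 6.3.2 is general. Nor does 6.3.2 say that its CI is for the difference between arms.

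**Early effects are studied elsewhere.** A reader might infer that the early-effect question goes unanswered, or that M6min is compared only at week 12. The documents support neither. Activity is compared weekly and two-weekly, PGA at weeks 4, 8 and 12, and the M6min responder proportion without a week-12 limit. Table 14.2-35 also plans a time-course fit for M6min by arm. The point is confined to the two continuous changes. A reader might also take the restriction as deliberate because PGA names all three weeks; the table list points the other way.

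**Protocol 9.5.1 promises a test for each endpoint, not each visit, and the 6MWT objective does not itself name an arm comparison.** Both are fair. The M6min objective does name one, however, and for 6MWT a test at week 12 alone adds nothing to the co-primary.

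**The second test decides nothing.** Correct: secondary tests are exploratory, and the Hochberg procedure in SAP 4.2 covers only the two primary hypotheses.

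**The 19% rests on undocumented inputs.** Also correct: 20 m is illustrative, and the documents give no correlation for 6MWT.

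**Conclusion.** The point holds as an inconsistency within the SAP, with a cheap remedy. Section 6.3.6 limits the arm comparison of 6MWT change and continuous M6min change to week 12, against objectives that name weeks 4, 8 and 12 and a table list that analyses 6MWT at all three. For 6MWT, the text states no contrast for the only new visits and adds a second test of the co-primary change. At ρ = 0.5 that test's SE is 9.31 m against 8.06 m for the ANCOVA. The choice between t-test and Wilcoxon depends on normality, for which SAP 6.3.2 gives no criterion.

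The risk of conflicting week-12 results is small at the plan's effect of 35 m, about 3%. It rises to about 19% at 20 m, or 7% to 24% for ρ from 0.9 to 0.3. A reader might infer a loss of confirmatory alpha from the duplicate test; the documents do not support that, because it stays outside the primary decision.

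These figures assume 300 analysed per arm, 114 m as the SD of change (SAP 4.2 does not label it so) and the same SD at each visit. The value ρ = 0.5 is borrowed from the actigraphy planning in SAP 4.2. The Wilcoxon option was not simulated.

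**What to change.** In SAP 6.3.6, before database closure and unblinding:

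- **6MWT, weeks 4 and 8:** replace the week-12-only sentence with a between-arm estimate and 95% CI at each week, from the primary ANCOVA model (baseline distance and NYHA class) or one repeated-measures model with the same covariates.
- **6MWT, week 12:** refer to the primary ANCOVA. Drop the t-test/Wilcoxon, or label it supportive.
- **Continuous M6min:** compare change between arms at weeks 4, 8 and 12, adjusted for baseline.
- **Tables 14.2-11 and 14.2-22:** make the labels match this text.

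The cost is SAP wording and a few rows in tables already planned; no new data are needed. The downside is a few more exploratory estimates without multiplicity control, which the report should say.

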6.3.5 Primary Efficacy analysis

One of the primary end-points is the change from baseline to 'end of study' in the 6-minute walking test.

The aim of the primary analysis of this study is to assess differences between sacubitril/valsartan and enalapril patients with respect to the primary endpoint in the FAS population excluding the patients who have an AE/SAE (non-HF related) during/around the 6-minute walking test which directly is causally linked to the 6-minute walking test performance.

Change from baseline values will be summarized. The comparison of treatment groups will be carried out using an ANCOVA model adjusting for treatment and baseline NYHA class (NYHA II vs. III/IV) and the baseline value as covariates.

The following hypothesis will be tested:

$H_0: \mu_0 = \mu_1$ vs. $H_1: \mu_0 \neq \mu_1$

Where 0 corresponds to treatment with sacubitril/valsartan and 1 corresponds to treatment with enalapril.

$6MWT_0$ = 6-minute walking test at baseline (week 0).

$6MWT_1$ = 6-minute walking test EOS (week 12).

$6MWT_{ch}$ = change in 6-minute walking test from baseline ($6MWT_1 - 6MWT_0$).

$GROUP_k$ = treatment group.

$NYHA_{0i}$ = baseline NYHA class

ANCOVA model:

$6MWT_{chi} = \mu + GROUP_k + 6MWT_{0i} + NYHA_{0i} + e_{ik}$

where:

$6MWT_{chi}$: change in 6-minute walking test for each subject i.

μ : global mean

$GROUP_k$: treatment group

$6MWT_{0i}$ = 6-minute walking test baseline (week 0) value for each subject i.

$NYHA_{0i}$ = NYHA class baseline value for each subject i.

e_{ik} : associated unobserved error term.

Other primary endpoint is the change from baseline to 'end of study' in mean daily non-sedentary daytime activity (defined as ≥ 178.50 activity counts per minute) as calculated by the MotionWatch 8 accelerometer device. Baseline is defined as the average minutes per day in non-sedentary daytime activity over 2 weeks (week -2 to week 0) prior to randomization and 'end of study' is defined as the average minutes per day in non-sedentary daytime activity between week 10 to week 12.

The aim of the primary analysis of this study is to assess differences between sacubitril/valsartan and enalapril patients with respect to the primary endpoint in the FAS with MI.

Change from baseline values will be summarized. The comparison of treatment groups will be carried out using an ANCOVA model adjusting for treatment and baseline NYHA class (NYHA II vs. III/IV) and the baseline value as covariates.

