Proportion of patients with improved symptoms of HF as assessed by PGA, number and proportion will be tabulated at week 4, week 8 and week 12. The comparison of patient groups will be presented and analyzed using a chi-square test or Fisher's exact test, where applicable.

Change from baseline in mean daily non-sedentary daytime activity in weekly and two-weekly intervals will be summarised. The comparison of patient groups will be analyzed using a two sample (independent group) t-test or a non-parametric Mann–Whitney–Wilcoxon (Wilcoxon rank sum) test, where applicable.

Proportion of patients at weekly and two-weekly intervals who show increased levels ($\geq 10\%$ increase) of mean daily non-sedentary daytime physical activity compared to baseline will be tabulated. The comparison of patient groups will be presented and analyzed using a chi-square test or Fisher's exact test, where applicable.

Change from baseline in mean daily light and moderate-to-vigorous non-sedentary daytime physical activity between baseline and different time points under treatment (weekly or two-weekly from week 0 to week 12) will be summarised. The comparison of patient groups will be analyzed using a two sample (independent group) t-test or a non-parametric Mann–Whitney–Wilcoxon (Wilcoxon rank sum) test, where applicable.

Total weekly time spent in non-sedentary daytime physical activity will be summarised by week, from week 0 to week 12. The comparison of patient groups will be analyzed using a two sample (independent group) t-test or a non-parametric Mann–Whitney–Wilcoxon (Wilcoxon rank sum) test, where applicable.

[figure not shown]
Total weekly time spent in light non-sedentary daytime physical activity will be summarised by week, from week 0 to week 12. The comparison of patient groups will be analyzed using a

[figure not shown]
two sample (independent group) t-test or a non-parametric Mann–Whitney–Wilcoxon (Wilcoxon rank sum) test, where applicable.

Total weekly time spent in moderate-to-vigorous non-sedentary daytime physical activity will be summarised by week, from week 0 to week 12. The comparison of patient groups will be analyzed using a two sample (independent group) t-test or a non-parametric Mann–Whitney–Wilcoxon (Wilcoxon rank sum) test, where applicable.

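### SAP 6.3.6 tests continuous secondary endpoints without the baseline and NYHA adjustment used for the primaries, and the PGA score without its order, which costs precision in exploratory comparisons

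*SAP*

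**What the plan says.** Both primary comparisons in SAP 6.3.5 are "carried out using an ANCOVA model adjusting for treatment and baseline NYHA class (NYHA II vs. III/IV) and the baseline value as covariates". SAP 6.3.6 uses logistic regression with the same covariates for four week-12 responder endpoints: the three 6MWT gains of at least 30 m (overall and in two baseline-distance subsets) and the activity gain of at least 10%.

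The continuous secondary endpoints in SAP 6.3.6 are handled differently:

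- **Interval activity change:** "in weekly and two-weekly intervals will be summarised. The comparison of patient groups will be analyzed using a two sample (independent group) t-test", or a Wilcoxon rank-sum test where applicable. The same wording covers light and moderate-to-vigorous activity and the three weekly totals.
- **6MWT:** "Score of 6-minute walking test will be summarised at baseline, week 4, week 8 and week 12", and then "The comparison of patient groups at week 12 compared to baseline will be analyzed using a two sample (independent group) t-test" or the Wilcoxon test. M6min is tested in the same way.
- **PGA score (seven ordered levels):** "The comparison of patient groups at week 4, week 8 and week 12 will be analyzed using a chi-square test" or Fisher's exact test. A yes/no version is also planned: "Proportion of patients with improved symptoms of HF as assessed by PGA, number and proportion will be tabulated".

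SAP 6.5 does not restore the adjustment; it only points back to 6.3.4 and 6.3.5. Protocol 5.3 stratifies randomisation by NYHA class. Protocol 9.5.1 calls the secondary tests exploratory and leaves the procedures to the SAP.

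**The concern.** The baseline values are already collected and derived, including those for the weekly totals (SAP Table 14.1-10), and NYHA class is the randomisation stratum. The SAP uses both where it fits a model and drops both for the endpoints that describe the time course, the intensity of activity and M6min. It gives no reason for the difference.

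A two-sample test on change keeps baseline variation that ANCOVA would remove. A chi-square test on seven ordered levels spreads its power over every possible difference in pattern, when the question is whether patients shift towards improvement. At stake is how precisely the exploratory results are estimated. The primary results, the sample size and the error rates are not affected.

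**Working it through.** **1. The plan's own figure.** SAP 4.2 uses a difference of 20 min/day, SD 70, two-sided 5% and 90% power. The normal approximation gives 2 × (1.960 + 1.282)² × 70²/20² = 257.4, so 258 per arm. The noncentral t gives 259, as stated. SAP 4.2 ties the change SD of 70 to a visit SD of 70 and a correlation r of 0.5: 70 × √(2 × (1 − 0.5)) = 70.

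**2. Change scores.** In units of the visit variance, the variance of change is 2(1 − r) and the ANCOVA residual variance is 1 − r². The ratio is (1 + r)/2, so the saving is (1 − r)/2. The half-width is t(0.975, 516) × SD × √(2/259), which is 0.1726 × SD. The visit SD of 70 is assumed to hold for every interval.

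| r | Variance saving | Half-width, change (min/day) | Half-width, ANCOVA (min/day) |
|---|---|---|---|
| 0.3 | 35% | 14.3 | 11.5 |
| 0.5 | 25% | 12.1 | 10.5 |
| 0.7 | 15% | 9.4 | 8.6 |
| 0.8 | 10% | 7.6 | 7.3 |

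The planning value r = 0.5 refers to the week-12 comparison. It does not fix r for a single week against a 7-day baseline, so a value below 0.5 is possible there and the saving would be larger. The separate gain from NYHA cannot be computed, because the documents give no association between NYHA class and outcome.

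**3. Weekly totals.** SAP 6.3.6 names no change from baseline for these, while Tables 14.2-19 to 14.2-21 list absolute values and change. If the absolute value is tested, the variance falls from 1 to 1 − r², a saving of r²: 25%, 49% and 64% at r = 0.5, 0.7 and 0.8. The documents give no r for weekly totals, so these are assumed values.

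**4. Moderate-to-vigorous activity.** SAP 4.2 gives 46 (SD 35) and 41 (SD 30) min/day, so the SD is about three quarters of the mean (35/46 = 0.76; 30/41 = 0.73). Such a non-negative measure is probably right-skewed. The simulation used lognormal data with these moments (log-SD 0.676 and 0.655), 259 per arm, 4000 runs and assumed log-scale r of 0.5, 0.7 and 0.8. The effect was set so that Wilcoxon on change has about 80% power.

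| Effect | r | Wilcoxon on change | Plain ANCOVA | Baseline-adjusted rank test (Quade) |
|---|---|---|---|---|
| Additive | 0.5 | 79.0% | 73.7% | 97.1% |
| Additive | 0.7 | 78.6% | 67.8% | 95.9% |
| Additive | 0.8 | 80.1% | 64.5% | 94.7% |
| Proportional | 0.5 | 79.0% | 86.1% | 91.4% |
| Proportional | 0.7 | 78.1% | 80.4% | 87.8% |
| Proportional | 0.8 | 80.3% | 79.2% | 89.0% |

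Type I error was 4.4–5.6% throughout. The ranked variable matters: in repeat runs, Quade on the post-baseline value had 83–99% power and Quade on change 79–94%. The rank test and ANCOVA disagreed on significance in about 11–30% of simulated trials.

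**5. PGA.** A 1-df test with 90% power has noncentrality (1.960 + 1.282)² = 10.51. The same noncentrality gives 67% on 6 df, or 74% on 4 df if two levels are empty. As a cross-check, 5000 runs were simulated with 259 per arm and an assumed control distribution of 8/17/25/32/10/5/3% from best to worst. The yes/no test counts the first three levels as improved, which is also an assumption.

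| Common odds ratio | Chi-square, 7 levels | Wilcoxon | Improved yes/no |
|---|---|---|---|
| 1.3 | 20% | 39% | 31% |
| 1.5 | 45% | 72% | 62% |
| 1.7 | 70% | 92% | 84% |

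**The case against.** The strongest reply is that this is a preference about efficiency. Protocol 9.5.1 makes the tests exploratory and leaves their form to the SAP, so the SAP complies. Randomisation keeps the unadjusted tests valid. The gain shrinks as r rises, to a 5% narrower interval at r = 0.8. Other comparisons cover the same ground: "Proportion of patients at weekly and two-weekly intervals who show increased levels", "Proportion of patients with increased M6min (an actigraphy-based measure of the peak six minutes of daytime physical activity) compared to baseline", and the fitted-curve parameter in Tables 14.2-34 and 14.2-35. The planned improved proportion recovers part of the PGA loss. SAP 6.3.2 does not clearly promise an interval for a between-group difference, so the half-widths above express the precision of the comparison and do not correspond to a named output. All of this stands, and it limits the weight of the point. It gives no reason to leave available baseline data unused. The additional proportions are themselves tested unadjusted.

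A reader might infer more than the documents support:

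- **That the protocol is breached because 6.3.6 tests 6MWT and M6min at week 12 only.** Protocol 9.5.1 asks for tests of all secondary endpoints, not at every visit. Tables 14.2-11 and 14.2-22 cover weeks 4, 8 and 12, so the mismatch is editorial.
- **That unadjusted repeats of week-12 6MWT change and week 10–12 activity undermine the primaries.** SAP 6.3.7 names the main analysis for each and already plans several further versions, so one more p-value needs only a label.
- **That plain ANCOVA is always the better test.** The moderate-to-vigorous simulation shows otherwise.
- **That M6min is skewed.** The documents give no distribution for it.

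**Conclusion.** The point holds as a minor, worthwhile improvement. The continuous secondary endpoints are tested without covariates that the SAP uses elsewhere, and the PGA score is tested without its order. For change scores the avoidable variance is 25% at the SAP's planning correlation, 15% at r = 0.7 and 10% at r = 0.8. The 25% should not be read as a ceiling: it is exceeded if r is below 0.5 for single weeks, or if weekly totals are tested as absolute values with r above 0.5. For the PGA score, 90% power for a consistent ordered shift becomes about 67%.

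Nothing here suggests inflated error, a changed sample size or doubt about either primary result. The description of the planned tests is certain. The sizes rest on a visit SD of 70 in every interval, assumed correlations outside the week-12 activity comparison, a lognormal shape for moderate-to-vigorous activity, and a consistent ordered PGA effect.

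**What to change.** Before database closure, amend SAP 6.3.6 as follows:

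- **Continuous secondary endpoints:** replace the t-test/Wilcoxon choice with ANCOVA on treatment, the matching baseline value and baseline NYHA class. Protocol Table 2-1 sets the baseline: the last 7 days for weekly intervals and 14 days for two-weekly intervals. For weekly totals, ANCOVA gives the same treatment difference on absolute values or on change.
- **Moderate-to-vigorous activity:** name one baseline-adjusted rank test (Quade) on the post-baseline value as the test, with the ANCOVA estimate as description. State in advance that the two can disagree on significance.
- **PGA score:** use a Wilcoxon test stratified by NYHA class, and keep the improved proportion.
- **Week-12 6MWT change and week 10–12 activity:** label these secondary results as supportive of the primary analysis. Do not put the multiple-imputation primary estimate into the activity series, which Table 14.2-16 plans on the FAS without multiple imputation.

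The cost is SAP wording and minor programming, since the covariates are already available. The downside is that adjusted rather than raw differences are tested; the raw summaries stay in the tables.
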